6.1 Study Period

- 1) 24 months from approval of the clinical trial protocol
- 2) Recruiting period: 7 months
- 3) Follow-up period: 12 months from baseline (week 0) to final visit
- 4) Long term follow-up visit: 24 months following administration of CARTISTEM®

6.2 Subject Selection Criteria

- 1) Inclusion Criteria
- A. Patients with an intended- to- treat single focal, full-thickness cartilage defect (ICRS [International Cartilage Repair Society] Grade 3 or 4) of the knee as a result of ageing,

CARTISTEM®

page 19 of 137

CONFIDENTIAL: These all contents herein are the sole property of MEDIPOST Co., Ltd. Any reproduction or distribution of this document without the written consent of MEDIPOST Co., Ltd is prohibited. Copyright © 2017 MEDIPOST Co., Ltd.

trauma, or degenerative diseases

- B. Age \geq 18 years old
- C. Size of the articular cartilage lesion is $\ge 2 \text{ cm}^2$
- D. Swelling, tenderness and active range of motion \leq Grade II
- E. Joint pain : 20-mm 60-mm on VAS (Visual Analog Scale) at the time of Screening
- F. Appropriate blood coagulation, kidney and liver function laboratory parameters:
 - ✓ PT(INR) < 1.5, APTT <1.5×control
 - ✓ Creatinine \leq 2.0 mg/dL, Albumin \leq trace in urine dipstick test
 - ✓ Bilirubin \leq 2.0 mg/dL, AST/ALT \leq 100 IU/L
- G. Ligament instability \leq Grade II
- H. Lower extremity alignment within 5 degrees of the neutral weight bearing axis
- I. No meniscal surgery within the past 3 months and more than 5mm of meniscal rim remaining
- J. Ability and willingness to fully participate in the post-operative rehabilitation program
- K. Subject is informed of the investigational nature of this study, voluntarily agrees to participate in the study, and signs an IRB-approved informed consent prior to performing any of the screening procedures
- L. Body Mass Index (BMI) \leq 35 kg/m²
- 2) Exclusion Criteria
- A. Patients that have been treated previously and are asymptomatic
- B. Avascular necrosis / osteonecrosis
- C. Autoimmune or inflammatory joint disease
- D. History of infection within the past 6 weeks
- E. Surgery or radiation therapy within the past 6 weeks
- F. Serious medical co-morbidities which would otherwise contraindicate surgery, as determined by the investigator
- G. Currently pregnant or nursing
- H. Psychotic diseases, epilepsy, or any history of such diseases

CARTISTEM®

page 20 of 137

CONFIDENTIAL: These all contents herein are the sole property of MEDIPOST Co., Ltd. Any reproduction or distribution of this document without the written consent of MEDIPOST Co., Ltd is prohibited. Copyright © 2017 MEDIPOST Co., Ltd.

- I. Current abuse of alcohol (> 10 drinks weekly) and/ or regular exposure to other substances of abuse; currently an active smoker
- J. Chronic inflammatory articular diseases such as rheumatoid arthritis
- K. Enrolled in any other clinical trials within the past four weeks
- L. Administered immunosuppressants such as Cyclosporin A or azathioprine within the past 6 weeks
- M. Ligament instability > Grade II
- N. Uncorrected significant lower extremity malalignment (i.e. > 5 degrees)
- O. (Sub-) Total meniscectomy (<5mm rim remaining)
- P. Corticosteroid or viscosupplementation injection to the affected knee in the past 3 months
- Q. Principal investigator considers inappropriate for the clinical trial due to any reasons other than those listed above

6.3 Number of Subjects

1) Estimated Number of Patients

This study requires 12-18 patients (6-9 patients per arm depending on rate of DLT) for two different dose ranges (Dosage A: defect sizes of 2-5 cm² and Dosage B: defect sizes of above 5 cm²).

2) Target Number of Subjects and Rationale

This is a phase I/IIa clinical trial to evaluate safety and exploratory efficacy of the investigational drug product. Therefore, it is not considered critical to base the number of subjects on formal statistical power calculations. Six patients at each dose cohort enrolled sequentially are considered sufficient for this study. This study will be performed with two dose ranges, on the basis of existing pre-clinical test results. Initially, 6 patients with defect sizes of 2-5 cm² will be enrolled in Dosage A. If no DLT is seen during Dosage A, another 6 patients with larger defect sizes (above 5 cm²) will be recruited for Dosage B of the study. There could be a need for an intermediate dose or up to 6 additional patients, based on the rate of DLT seen.

CARTISTEM®

page 21 of 137

CONFIDENTIAL: These all contents herein are the sole property of MEDIPOST Co., Ltd. Any reproduction or distribution of this document without the written consent of MEDIPOST Co., Ltd is prohibited. Copyright © 2017 MEDIPOST Co., Ltd.

1) Initial Administration Dosage and Rationale

It is somewhat well understood by developers and regulators of living cell therapies that for products like CARTISTEM[®] administered locally into an anatomical defect there is no simple extrapolation of a safe starting dose in humans based primarily upon body surface area calculations derived from animal studies.

In addition, dose determinations in this clinical setting should take into account the surface area of the cartilage defect such that all NOAEL values should be converted into a unit quantity (cells/cm²) at the application site. This approach applies to most therapeutics administered into anatomical compartments that have little subsequent distribution outside of the compartment; it is recommended that doses are normalized between species according to the compartmental volumes and amount of the therapeutic product.

Support for the range of CARTISTEM[®] doses (0.5×10^7 cells to 2.25×10^7 cells) to be evaluated for safety and efficacy in this phase I/IIa study comes from both preclinical studies and clinical results in humans (comprised of a completed Phase I/II study in Korean patients with articular cartilage defects (N=7) and an ongoing Phase III study in Korean patients (N=50), as follows:

NOAELs for CARTISTEM[®] have been determined in the rat (Study No. B04001; NOAEL = $3x10^7$ cells per mL; > $1x10^7$ cells per cm²) and the rabbit (Study No. B04004; NOAEL = $1.5x10^7$ cells per mL; > $0.3x10^7$ cells per cm²); however, it is possible that the design of these studies did not allow for a proper assessment of the NOAEL due to limitations on the density of cells administered, and an overall very low toxicity of the hUCB-MSC in the species examined.

No treatment-related SAEs have been reported in seven patients who participated in a phase I/II Korean study and 50 patients currently enrolled in an ongoing phase III Korean study; all of these patients have received single administrations of 0.25×10^7 cells/cm² (0.5 ml/cm² with $0.5x10^7$ MSC/mL) up to a maximum of $2.25x10^7$ total MSC; this number of cells represents a much higher dose than the NOAEL ($10x10^7$ MSC per mL) derived from CARTISTEM® page 22 of 137

CONFIDENTIAL: These all contents herein are the sole property of MEDIPOST Co., Ltd. Any reproduction or distribution of this document without the written consent of MEDIPOST Co., Ltd is prohibited. Copyright © 2017 MEDIPOST Co., Ltd.

Study B04001 (GLP repeat-dose toxicology study in rats).

Based on these findings (for further discussion, please see the Investigator's Brochure), MEDIPOST has selected a single administration of CARTISTEM[®] at 0.25×10^7 cells/cm² (0.5 mL/cm² with 0.5×10^7 hUCB-MSC/mL), with both the volume and total number of hUCB-MSC administered to patients being a function of the defect size.

Similar products available on the market include CARTICEL[®] manufactured by Genzyme Biosurgery, an autologous cultured chondrocyte product approved by the US-FDA. Clinical studies of CARTICEL[®] were conducted at dose levels ranging from 0.64×10^6 cells/cm² up to 3.3×10^6 cells/cm² for the 1.2×10^7 cells/0.4mL product. Meanwhile, Chondron, the autologous chondrocyte regeneration therapy of Cellontech, Korea, is a 1.2×10^7 cells/0.4mL product which is applied at a ratio of 0.1 mL for every 1 cm² of cartilage defect. For cartilage defects greater than 4 cm² in size, the entire vial is administered.

Both CARTICEL[®] and Chondron are autologous chondrocyte therapies, with limits in cell proliferation and maximum number of cells that can be achieved in the defect. In other words, the limited cell number is a challenge and it is difficult to determine a constant cell concentration per unit area in larger defect sizes. Also, there are potentially large differences in cell potency since the starting materials/living cells are derived in a patient-specific manner and, therefore, typically vary greatly from patient to patient.

CARTISTEM[®] can be differentiated from these two products because it is an off-theshelf allogeneic-unrelated cellular therapy that allows a consistent application of the most effective cell concentration per area of defect throughout the entire lesion with a constant cell concentration.

Against this background, the most scientific and logical approach for the study would be to perform the clinical trial using two different cell concentrations of 0.5×10^7 cells/mL and 1.0×10^7 cells/mL. However, it was deemed ethically inappropriate to subject a treatment group to a relatively-less effective dose. Therefore, a single cell concentration expected to be the more effective of the two was first chosen through a preclinical study and adopted for CARTISTEM[®] page 23 of 137

CONFIDENTIAL: These all contents herein are the sole property of MEDIPOST Co., Ltd. Any reproduction or distribution of this document without the written consent of MEDIPOST Co., Ltd is prohibited. Copyright © 2017 MEDIPOST Co., Ltd.

this clinical trial. The total volume of administration was determined by size of the lesion.

CARTISTEM[®], consisting of mesenchymal stem cells and sodium hyaluronate, will be applied at a dose of 0.5 mL/cm². The administered dose is, therefore, a function of the defect size. It will be administered into the cartilage defect by open surgery.

The following chart provides determination of CARTISTEM[®] dosage relative to the defect size (derived from nonclinical studies and prior human experience):

Study	Defect Size	Volume of Dose	Total Cell Number	Device Dosage		
Phase	Defect Size	volume of Dose	(hUCB-MSC)	(Sodium hyaluronate)		
	2 cm^2	1.0 mL	0.5×10^7 cells	40 mg		
А	3 cm ² 1.5 mL		0.75×10^7 cells	60 mg		
	4 cm^2	2.0 mL	1.0×10^7 cells	80 mg		
	5 cm^2	2.5 mL	1.25×10^7 cells	100 mg		
	6 cm^2	3.0 mL	1.5×10^7 cells	120 mg		
В	7 cm^2	3.5 mL	1.75×10^7 cells	140 mg		
Б	8 cm ²	4.0 mL	2.0×10^7 cells	160 mg		
	9 cm ² ~	4.5 mL~	2.25×10^7 cells~	180 mg ~		

6.5 Dose Escalation

This clinical trial will employ the following dose escalation scheme:

[figure not shown]
A total of 12-18 patients will be enrolled and treated with CARTISTEM[®] for dose limiting toxicity (DLT) evaluation. Initially, 6 patients with lesion sizes of $2 - 5 \text{ cm}^2$ will be assigned to Dosage A and treated with $0.5 - 1.25 \times 10^7$ MSCs; if dose limiting toxicity is not observed at the 3 month time point for the first clinical efficacy evaluation, then another 6 patients with lesion sizes of above 5 cm² will be assigned to Dosage B and treated with more than 1.25 x 10^7 MSCs for further safety evaluation. If a DLT occurs to one or two patients of the group treated with the dosage A, 3 more patients will be assigned to dosage A. If DLT happens to 3 of the patients who were treated with the dosage A or above, this study will be halted and the FDA and IRB will be notified. The Independent Data Monitoring Committee will perform a comprehensive review of safety (see Section 9.1).

CARTISTEM®

page 24 of 137

CONFIDENTIAL: These all contents herein are the sole property of MEDIPOST Co., Ltd. Any reproduction or distribution of this document without the written consent of MEDIPOST Co., Ltd is prohibited. Copyright © 2017 MEDIPOST Co., Ltd.

If no DLT occurs to any of the dosage A patients, another 6 patients with larger defect sizes will be enrolled and assigned to dosage B. In case of no DLT observed, a total of 12 patients will be enrolled for safety and efficacy evaluation. However, 18 patients could be enrolled if DLT occurs to two patients. If DLT occur 3 or more patients treated with Dosage B, this study will be halted and the FDA and IRB will be notified. The Independent Data Monitoring Committee will perform a comprehensive review of safety (see Section 9.1).

CARTISTEM®

page 25 of 137

CONFIDENTIAL: These all contents herein are the sole property of MEDIPOST Co., Ltd. Any reproduction or distribution of this document without the written consent of MEDIPOST Co., Ltd is prohibited. Copyright © 2017 MEDIPOST Co., Ltd.

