6.6 Definition of Maximum Permissible Dose and Method of Dose Escalation

Dose Limiting Toxicity (DLT): DLT is defined as toxicity or events of Grade 3 or higher (80 points or higher against pain) in two or more events at the surgery site among swelling, tenderness, range of motion, and pain in any one visit. DLT is also defined as adverse drug reaction of Grade 3 or higher in the Common Toxicity Criteria Adverse Events (CTCAE), Version 4.0, with the exception of the following events and that they are unresolved for 7 consecutive days, despite medical interventions:

- ✓ Abnormal results in lab test (Acidosis, Hyponatremia, Hyperbilirubinemia, etc.)
- ✓ Fatigue, defined as not relieved by rest; limiting self-care ADL
- ✓ Pain, defined as severe pain; limiting self-care ADL
- ✓ Headache, defined as severe pain in various parts of the head, limiting self-care ADL Fever, defined as > 40.0 degrees C (> 104.0 degrees F) for > 24 hours

Maximum Tolerated Dose (MTD): If DLT occurs in 2 or fewer patients at the Dosage B level, the MTD will be Dosage B. If DLT occurs in 3 or more patients treated with Dosage B then the MTD will be Dosage A. If DLT occurs in 3 patients treated with Dosage A then the MTD will not have been determined in this study design.

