8.4.3 Evaluation of Adverse Events & Toxicity

Any adverse events (AE) or toxic reactions of each participating subject will be evaluated throughout the course of the study and at each follow up visit (from Day -2 to the end-of-study visit). Any adverse events or serious adverse events will be managed, investigated, and reported according to the procedures described in the following sections:

✓ Adverse Events

When an adverse event is either observed by the investigator or reported by a subject, the investigator, regardless of the relationship of the AE to the investigational product, will record name and type of the adverse event, the severity, dates of onset and resolution of the event, the investigator's opinion on the relationship between the investigational product and the adverse event, and whether or not the event was an SAE (serious adverse event) on the case report form (CRF).

The principal investigator or the trial coordinator will carry out follow-up observations for all subjects with adverse events until the symptoms subside and the abnormal clinical test results are returned to normal, or until a satisfactory explanation can be given for the observed changes. If and when there is such a request from the sponsor, a progress report on the adverse event will be submitted to the trial coordinator.

✓ Serious Adverse Events

A serious adverse event is defined as any untoward medical occurrence at any dose that causes death, life-threatening condition, in-patient hospitalization or prolongation of existing hospitalization, persistent or significant disability/incapacity, a congenital anomaly/birth defect, or another important medical event (see below).

CARTISTEM®

CONFIDENTIAL: These all contents herein are the sole property of MEDIPOST Co., Ltd. Any reproduction or distribution of this document without the written consent of MEDIPOST Co., Ltd is prohibited. Copyright © 2017 MEDIPOST Co., Ltd

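### Once Dosage B has opened, the visible text states no rule that holds B dosing or calls an IDMC review if one or two Dosage A patients then have a first DLT

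*Combined protocol and SAP*

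**What the plan says.** **The gate.** Section 6.5 opens Dosage B if "dose limiting toxicity is not observed at the 3 month time point for the first clinical efficacy evaluation". The synopsis gives the same period as 12 weeks. Two other sentences carry no date: "If no DLT occurs to any of the dosage A patients, another 6 patients with larger defect sizes will be enrolled" (6.5) and "If no DLT is seen during Dosage A, another 6 patients with larger defect sizes" (6.3).

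**What counts as a DLT, and for how long.** One branch of the definition in 6.6 needs Grade 3 or higher in "two or more events at the surgery site among swelling, tenderness, range of motion, and pain in any one visit"; the other is a Grade 3 or higher adverse drug reaction, with listed exceptions. Neither has an end date. Section 8.4.3 has toxicity evaluated "from Day -2 to the end-of-study visit", and the flow chart has visits at Week 24, Month 12 and Month 24.

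**Response to one or two Dosage A DLTs.** Section 6.5: "DLT occurs to one or two patients of the group treated with the dosage A, 3 more patients will be assigned to dosage A". It adds: "However, 18 patients could be enrolled if DLT occurs to two patients". Section 6.3 mentions a possible intermediate dose or up to 6 additional patients.

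**Halt.** Section 6.5: "If DLT happens to 3 of the patients who were treated with the dosage A or above, this study will be halted". The FDA and IRB are then notified, and the sentence on a comprehensive IDMC review follows. The same pairing appears for three or more DLTs in Dosage B.

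**Oversight.** Section 9.1 provides periodic IDMC review and sends serious adverse events to the committee. The charter (Appendix 5) plans quarterly calls, flexible with enrolment. It requires meetings for a protocol revision, before Dosage B starts, and for the draft final report. Its stopping rules are to be set before the first data review and are not given.

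**The concern.** The gate looks at the first 12 weeks of a follow-up that runs to 12 months, with a further visit at 24 months. Suppose a Dosage A patient has a first DLT at Week 24, when some Dosage B patients have been implanted and others have not. The same event at the gate would have made B wait while A was expanded. After the gate, the prose says only that A grows by three patients and that an intermediate dose may be needed. It does not say whether the next B patient may be dosed.

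B is the step up in total exposure (more than 1.25 × 10^7 cells, with the matching hyaluronate), and the synopsis says safety is assessed stepwise on that quantity. The product is placed in drilled bone by open surgery and cannot be taken back, so a review is worth most before the next B implant. Two centres could also read the gate differently.

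**Working it through.** **1. The plan's own figures.** 2 × 6 = 12 and 2 × (6 + 3) = 18, which reproduce the 12 to 18 patients in 6.3.

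**2. The rule before and after the gate.**

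| Dosage A DLTs | Seen at the gate | First seen after B opens, dated reading | First seen after B opens, undated reading |
|---|---|---|---|
| 1 of 6 (17%) | B waits; 3 more in A | 3 more in A, possible intermediate dose; B not mentioned | B enrolment stops |
| 2 of 6 (33%) | B waits; 3 more in A | as above | B enrolment stops |
| 3 | halt, IDMC review | halt, IDMC review | halt, IDMC review |

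At the gate, one or two DLTs delay B rather than close it, since up to 18 patients are allowed. The halt in the last row can be read as pooled across A and B, so two late A events plus one B event would reach it.

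**3. How much follow-up comes after the gate.** 12 / 52.18 weeks = 23% of the 12-month follow-up is covered by the gate; 77% comes later.

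**4. Does that follow-up overlap with B dosing?** Inputs: a 7-month recruiting period (6.1), which is 30.4 weeks; 6 patients per cohort (6.3); a 12-week wait after the last A dose; Week 24 visits (8.2). Assumptions: doses evenly spaced and no IDMC lag before B opens. Let L be the time from first to last dose in a cohort. Dose spacing is L/5, B opens at L + 12, the last B dose is at 2L + 12, and the A Week 24 visits run from week 24 to week 24 + L.

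- *Wait inside the 7 months:* 2L + 12 = 30.4, so L = 9.2. B opens at week 21.2 and the last B dose is at week 30.4. Visits fall at weeks 24.0, 25.8, 27.7, 29.5, 31.4 and 33.2. The first four fall during B dosing, with 4, 3, 2 and 1 B patients undosed.
- *Wait outside the 7 months:* 2L = 30.4, so L = 15.2. B opens at week 27.2 and the last B dose is at week 42.4. Visits fall at weeks 24.0, 27.0, 30.1, 33.1, 36.2 and 39.2. The last four fall during B dosing, with 5, 4, 3 and 2 undosed.

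Both schedules give 4 of 6. With an assumed lag of 0, 2, 4 or 6 weeks and all visits shifted by up to the ±14-day window, the range is 2 to 5 of 6, with 1 to 5 B patients undosed. With no lag, on-time Month 12 visits (from about week 52) come after the last B dose in both schedules, so Week 24 is the scheduled visit that matters.

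**The case against.** The case against is substantial, and most of it narrows the point.

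- **Unseen material.** The escalation figure in 6.5 is not shown, and the charter's stopping rules were still to be set. Either could hold the missing rule. A reader might infer that no safeguard would act on a late Dosage A DLT; the documents do not support that. They support only that the visible prose states no such rule.
- **The undated sentences.** Read as a continuing condition, they would stop B enrolment. A reader might infer that the plan plainly lets B continue; it does not. It leaves two readings open.
- **The IDMC sentence in 6.5.** It points to 9.1, which describes ongoing review with power to recommend revision or closure, so it could stand alone. But both times it follows a three-DLT halt, and no timing or trigger is given for one or two events.
- **Serious events.** Many Grade 3 reactions, including disabling loss of motion, would qualify as serious and reach the IDMC. What is left is mainly two Grade 3 surgery-site signs that are not judged serious.
- **Low stakes.** Cells per cm² are the same in A and B. Section 6.4 (initial dosage and rationale) reports 7 + 50 = 57 earlier patients, dosed up to 2.25 × 10^7 cells, with no treatment-related SAEs. This is reassuring, but it does not speak to non-serious DLTs, and the protocol itself chose to gate on total exposure.
- **Quarterly calls.** If calls kept a fixed 13-week spacing, 4 or 5 B patients could be implanted between a late event and the next call. That is a worst case. It depends on assumed accrual, and the charter makes meetings flexible with enrolment. It should not be read as an expected number.

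**Conclusion.** The point holds in limited form. On the dated reading, and in the text that can be seen, one or two first Dosage A DLTs after B opens neither hold B dosing nor require an IDMC review; both come only with the three-DLT halt. On the undated reading B enrolment stops. The plan should say which applies.

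The gap covers the period of B dosing only, and mainly non-serious surgery-site DLTs. Its probability cannot be computed, because no late-DLT rate is given. What can be shown is opportunity: 4 of 6 Dosage A Week 24 visits fall within B dosing with no lag, and 2 to 5 across the assumed lags and visit shifts. These counts rest on even accrual over 7 months, which the documents do not state. This is a worthwhile, inexpensive improvement; it does not show that the escalation scheme is unsafe. Confidence is medium, because the figure and the stopping rules are unseen.

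**What to change.** In 6.5, state that the condition for opening Dosage B is read at 12 weeks. Then add that any later event in a Dosage A patient that meets the DLT criteria, serious or not, while B is enrolling is sent promptly to the IDMC, and that no further Dosage B patient is dosed until the IDMC has reviewed it. Put the same rule in the charter's stopping rules. If the 6.5 figure already carries such a rule, the prose should repeat it.

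The cost is about two sentences in 6.5 and one in the charter, with no added patients or visits. The downside is a possible short wait in B dosing if a late event occurs. The rule asks for review before the next implant; it does not close Dosage B.
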